CLINICAL TRIAL PROTOCOL

Title: A Phase 1b dose-finding study of DDFPe in acute ischemic stroke

Protocol Number: NVX-208-AIS

UAMS IRB Number: 205529

Phase: 1b

Study Principal Investigator: [name]
University of Arkansas for Medical Sciences

Co-Principal Investigator: [name]
University of Arkansas for Medical Sciences

Sub-Investigator: [name]
University of Arkansas for Medical Sciences

IND Sponsor:
University of Arkansas for Medical Sciences (UAMS)
[name]
[name]

Clinical Site:
University of Arkansas for Medical Sciences
Little Rock, AR

Medical Monitors:
[name]
Professor and Chair
Department of Internal Medicine
University of Arkansas for Medical Sciences

[name]
Associate Professor
Department of Internal Medicine
University of Arkansas for Medical Sciences

Title: A phase 1b dose-finding study of DDFPe in acute ischemic stroke

PIs: [name] & [name]

Institution: UAMS

Sponsor: UAMS

Study Summary

Title	A Phase 1b dose-finding study of DDFPe in Acute Ischemic Stroke
Sponsor	University of Arkansas for Medical Sciences
Protocol Number	NVX-208-AIS
Phase	Phase 1b
Methodology	Randomized, placebo controlled, blinded escalating dose design; 6:2 DDFPe to placebo at each dose level
Rationale	To provide dosing guidelines for a Phase 2 study in patients who have an acute stroke
Study Duration	Approximately 18 months
Study Center(s)	University of Arkansas for Medical Sciences, Little Rock, AR
Primary Objective	To determine the maximum tolerated dose (MTD) of Dodecafluoropentane emulsion (DDFPe) in subjects with acute ischemic stroke (AIS)
Secondary Objective	To determine the safety of DDFPe in subjects who have experienced an AIS event
Number of Subjects	Up to 24 completed subjects
Diagnosis and Main Eligibility Criteria	
➤ Inclusion: ages 18years old or older, male or female, AIS with NIH Stroke Scale between 2 and 20➤ Exclusion: Severe cerebral hemorrhage or severe hemorrhagic stroke, intracranial surgery or major head trauma within 3 months, > 12 hours since onset of stroke symptoms, clinically significant cardiac or pulmonary disease, current anticoagulant therapy (except low doses of aspirin or low molecular weight heparin), pregnancy or breastfeeding
Study Product, Dose, Route, Regimen	Dodecafluoropentane emulsion (DDFPe) Dose Range: 0.05, 0.10, and 0.17 mL/kg (Maximum dose: 17 mL/dose) Route: Intravenous over 5-10 minutes every 90 ± 10 minutes x 3 doses Placebo - Intralipid® 20% IV fat emulsion Dose: Sterile 1:101 dilution of Intralipid® in aqueous sodium chloride (0.9% w/v) Route: Intravenous over 5-10 minutes every 90 ± 10 minutes x 3 doses
Duration of Administration	Approximately 3-4 hours
Reference Therapy	None
Primary Outcome Measures	DLT (dose limiting adverse events) including clinically significant changes in vital signs, peripheral oxygen saturation (pulse oximetry), clinical symptoms, NIH Stroke Scale, laboratory values, and ECG measurements, Grade 3 or higher scores on selected CTCAE 4 measures

Title: A phase 1b dose-finding study of DDFPe in acute ischemic stroke

PIs: [name] & [name]

Institution: UAMS

Sponsor: UAMS

ABBREVIATIONS

AE	Adverse Event
AIS	Acute ischemic stroke
ALT	Alanine Aminotransferase
ANOVA	Analysis of Variance
aPTT	Activated Partial Thromboplastin Time
AST	Aspartate Aminotransferase
AUC	Area under the Concentration vs. Time Curve
BP	Blood Pressure
BUN	Blood Urea Nitrogen
CL	Clearance
Cmax	Maximum Concentration
COPD	Chronic Obstructive Pulmonary Disease
CRF	Case Report Form
CT	Computed (Computerized) Tomography
CTCAE	Common Terminology Criteria for Adverse Events
DDFP	Dodecafluoropentane
DDFPe	Dodecafluoropentane emulsion
DBP	Diastolic Blood Pressure
DLT	Dose Limiting Toxicity
DSM	Data Safety Monitor
ECG	Electrocardiogram
FDA	Food and Drug Administration
HIPAA	Health Insurance Portability and Accountability Act
HR	Heart rate
IEC	Independent Ethics Committee
INR	International Normalized Ratio
IRB	Institutional Review Board
IV	Intravenous
LAR	Legally Authorized Representative
LFT	Liver Function Tests
mmHg	Millimeters of Mercury
mRS	modified Rankin Scale
mSec	Millisecond
MTD	Maximum Tolerated Dose
N/A	Not Applicable
ND	Not Done
NIH	National Institutes of Health
NIHSS	National Institutes of Health Stroke Scale
NSAID	Non-Steroidal Anti-Inflammatory Drug
NYHA	New York Heart Association
OTs	Oxygen Transporters
PHI	Personal Health Information
PTB	PE-Telomer-B
RR	Respiratory Rate

Title: A phase 1b dose-finding study of DDFPe in acute ischemic stroke

PIs: [name] & [name]

Institution: UAMS

Sponsor: UAMS

SAE	Serious Adverse Event
SBP	Systolic Blood Pressure
SD	Standard Deviation
Tmax	Time at Which the Maximum Concentration (Cmax) Occurs
tPA	Tissue Plasminogen Activator

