2.0 Objectives

2.1 Primary Objective

The primary objective of this study is to establish the Maximum Tolerated Dose (MTD) of DDFPe given intravenously at intervals of 90 ± 10 minutes x 3 doses within 12 hours after subjects have had a documented Acute Ischemic Stroke (AIS).

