5.5 Administration of the Investigational Product

For each cohort, the dose of DDFPe or placebo will be calculated based on body weight according to the table in [Appendix 2](#). Before administration, the drug will be prepared for injection per instructions in the Pharmacy Manual. DDFPe will be administered intravenously over 5-10 minutes through an IV catheter placed in a peripheral vein or through a central venous catheter (Note: a central venous catheter will not be placed solely for the study). The site of the intravenous catheter through which the study drug is administered will be recorded in the research record. Doses will be administered by slow IV push. After the first dose, subsequent doses will be administered 90 ± 10 minutes after the end of the previous infusion. Administration of all doses should occur with the syringe in the vertical position assuring that any

product foaming in the syringe will float near the rubber seal of the syringe plunger (NOTE: THIS IS THE MOST CRITICAL SAFETY CONSIDERATION DURING INFUSION). The placebo will be placed in identical syringes and administered in the same way. The volume of drug product to be used from each syringe will be provided on the label from pharmacy. The start and stop times for each infusion will be recorded on the source documents. The volume of the infusion will also be recorded.

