6.2 Inclusion Criteria

6.2.1 Ages 18 years old or older

6.2.2 Diagnosis of AIS

6.2.3 Body weight \geq 45 kg

6.2.4 NIHSS between 2 and 20 inclusive.

6.2.5 Patient or LAR must be willing and able to understand the study and provide written informed consent

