7.3 Verification of Inclusion/Exclusion Criteria

After the consent process is complete, trained study personnel will review the Inclusion and Exclusion criteria with the subject/LAR. The following options are then possible:

- If the subject meets all criteria, they will be allowed to proceed with the study.
- If the subject fails to meet criteria, no further study-related procedures will be conducted.
- If the failure to meet criteria is minor, the investigator may choose to approach the Medical Monitor for a waiver. A waiver will be granted only if doing so will not place the subject at increased risk if allowed to participate in the study.

Study personnel will document the review of Inclusion and Exclusion Criteria on the appropriate form and place the signed form in the study file. The investigator will be notified of the results of the review.

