10.4 Exploratory Aim Analysis

There are a number of patient subgroups that could be of interest and might be expected to respond differently to DDFPe as evaluated by NIHSS scores:

- a. In those early patients who get some successful therapy and get DDFPe early at less than 3 hours from LKWT, the values should drop with the DDFPe and stay down with reperfusion. Late DDFPe uncertain.
- b. In those that get Rx and it fails, scores may perhaps go down with early DDFPe and come back up when it wears off. With late DDFPe little change is expected.
- c. In those that do not get reperfusion therapy and do get DDFPe in the first 3 hours, scores should go down but come back up when it wears off.
- d. In those that do not get reperfusion therapy and get DDFPe late, scores should not change much
- e. In those that get placebo, should see little change, early or late, unless they have successful reperfusion therapy or spontaneous reperfusion.

Fewer than 20% are likely to get IV tPA or IA reperfusion therapy of the total 24 patients; the patient numbers in any of these groups will be quite small, obviating the ability to make formal statistical comparisons or to draw conclusions about the impact of DDFPe therapy on outcome. This is a Phase I safety trial, and not designed to test treatment outcomes. As an exploratory analysis, we will compare the patients without reperfusion therapy, IV or IA, who got early DDFPe under 3 hours from LKWT, to placebo patients of similar characteristics. Due to the small sample sizes and because each of the proposed doses were effective in animal studies, we will ignore dose in this comparison.

We expect that the NIHSS values should drop with DDFPe but come back up after 5 or 6 hours and no change is expected in placebo. We will visually examine plots of the data for consistency with this hypothesis and if the sample sizes are sufficient, we will carry out nonparametric tests comparing the changes as exploratory analyses.

Those patients receiving DDFPe between 3 and 6 hours from LKWT could be another group of great interest, and we will make similar exploratory comparisons of this group with the two just described.

No claims of efficacy will be possible based on these limited data, but they may suggest directions for subsequent study.

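### The synopsis 12-hour limit is missing from the numbered eligibility criteria, and the hemorrhage and warfarin rules conflict between sections

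*Combined protocol and SAP*

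**What the plan says.** **Time limit.** The Study Summary, under main eligibility criteria, excludes patients "> 12 hours since onset of stroke symptoms". Section 2.1 describes the regimen as "x 3 doses within 12 hours after subjects have had a documented Acute Ischemic Stroke". In Section 6 the only inclusion item on the index stroke is "6.2.2 Diagnosis of AIS", with no time attached. Section 6.1 requires every inclusion and exclusion criterion to be met before enrollment, and 7.3 lets a subject who meets them all proceed. Section 7.3 adds: "Study personnel will document the review of Inclusion and Exclusion Criteria on the appropriate form". That form is not part of the document.

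**Timing elsewhere.** The exploratory analysis in 10.4 groups patients by LKWT, which is not in the abbreviation list and is read here as last known well time: those "who got early DDFPe under 3 hours from LKWT", and a further group, "Those patients receiving DDFPe between 3 and 6 hours from LKWT".

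**Hemorrhage.** Section 6.1 asks for a CT showing no hemorrhage. Section 6.3.3 excludes only severe hemorrhage and expressly permits Fisher Grade 1-2 subarachnoid changes and HI-1 or HI-2 transformation. The Study Summary and 7.5.2 also bar only severe hemorrhage.

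**Warfarin.** Section 5.6.1 names warfarin among the exceptions to the anticoagulant exclusion. Section 6.3.12 and the Study Summary give exceptions that do not include it.

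**The concern.** Staff screen from the numbered criteria. If a rule stands only in the synopsis, a check built on Section 6 will not catch a late patient, although dosing that patient would breach the protocol. In an acute stroke trial the entry window helps define the population in which the drug is tested for tolerability.

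Even a reader who finds the limit cannot apply it uniformly. There is no rule for a patient whose onset nobody saw, and the text does not settle whether the 12 hours must be met at enrollment, at the first dose or by the third.

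The other two conflicts are of the same kind: two parts of one protocol give different answers about the same patient. With at most 24 completed subjects, disputed eligibility in even a few would be awkward to resolve afterwards.

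**Working it through.** **1. Is the limit in the lists?** Reading each item:

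- Inclusion 6.2.1-6.2.5 covers age, diagnosis, weight, NIHSS and consent. Items limiting time since onset: 0 of 5.
- Exclusion 6.3.1-6.3.16: the only item on stroke timing is 6.3.4, which concerns a prior stroke within three months. Items limiting time since onset: 0 of 16.

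A patient presenting at, say, 15 hours can therefore satisfy all 5 + 16 = 21 items. Only 6.3.16, which rests on the investigator's judgment, could stop entry.

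**2. How long is the course?** Inputs are an infusion time of 5-10 min per dose (5.5, Appendix 4) and the interval rule in 5.5, "subsequent doses will be administered 90 ± 10 minutes after the end of the previous infusion", which gives 80-100 min. From the start of Dose #1 to the end of Dose #3 there are three infusions and two intervals:

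- Shortest: 3 × 5 + 2 × 80 = 175 min = 2.92 h
- Longest: 3 × 10 + 2 × 100 = 230 min = 3.83 h

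This reproduces the duration of administration in the Study Summary, "Approximately 3-4 hours".

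**3. What does 12 hours mean for dosing?**

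| Event governed by the limit | Latest start of Dose #1 | Latest end of Dose #3 |
|---|---|---|
| Enrollment | no dosing deadline follows | no dosing deadline follows |
| Start of Dose #1 | 12 h | 12 + 2.92 = 14.92 h to 12 + 3.83 = 15.83 h |
| End of Dose #3 (2.1 read literally) | 12 − 3.83 = 8.17 h to 12 − 2.92 = 9.08 h | 12 h |

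The last two readings differ in the Dose #1 cut-off by the length of the course, 2.9-3.8 h.

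**4. Hemorrhage and warfarin.** No arithmetic applies.

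- A patient with HI-1 on CT fails 6.1, is allowed by 6.3.3 and passes the CT review in 7.5.2. As written, the patient is both ineligible and eligible.
- A patient on warfarin falls under an exception in 5.6.1 and is barred by 6.3.12. If the qualifier about prophylactic dosing in 5.6.1 is taken to cover warfarin as well, the conflict remains, because 6.3.12 excepts no dose of warfarin.

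**The case against.** The strongest reply is that the limit exists. The synopsis is part of the protocol, and it states the threshold and the clock. Because it sits among the exclusions and 6.1 applies exclusions before enrollment, the natural reading is that it governs entry. The unseen form in 7.3 may already carry it. Section 2.1 is a loosely worded objective, not a dosing rule; 5.5 and 7.6 set no deadline for Dose #3, and 5.3.3 determines the MTD from DLT counts without reference to time from onset. On hemorrhage, the synopsis, 6.3.3 and 7.5.2 agree, so the intent is clear and 6.1 looks like one sentence out of step.

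Much of this stands, and it rules out several stronger readings that a reader might infer:

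- *That there are three competing eligibility clocks, or none.* The synopsis names symptom onset. The wording in 2.1 is compatible with it. LKWT is only a grouping variable in an exploratory analysis and sets no entry limit.
- *That a first dose after about 8-9 h violates the protocol.* This turns the phrasing of 2.1 into a dosing deadline that no operative section imposes.
- *That first doses could run to some particular hour after last known well.* The documents give no distribution of the gap between last known well and discovery, so any such range would rest on an assumed gap.
- *That late patients were actually treated.* The text cannot show this.

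The reply does not remove the core problem. Sections 6.1 and 7.3 send the reader to lists that omit the limit, and inferring that the limit applies at enrollment still leaves unwitnessed onset without a rule.

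**Conclusion.** The point holds as a conflict within the protocol's eligibility text and should be fixed. Following Section 6 alone admits a patient whom the synopsis excludes, and 6.1 and 6.3.3 give opposite answers for low-grade hemorrhage. The clock is named but lacks a rule for unwitnessed onset. The governed event can be inferred but is not stated, and the choice between first dose and completed course shifts the Dose #1 cut-off by 2.9-3.8 h.

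The timing figures rest only on the infusion times and intervals in 5.5 and Appendix 4. The number of subjects affected cannot be derived from the documents. The risks are not equal: the missing time limit could let in patients outside the intended window, and the warfarin exception, if followed, could admit patients whom 6.3.12 bars. Section 6.1 errs on the strict side, so the hemorrhage conflict threatens uneven screening or lost enrollment, not extra exposure. The warfarin discrepancy is the smallest of the three. A reader might infer that the MTD finding is compromised; the documents do not support that, because neither the escalation rule nor the DLT count uses time from onset.

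**What to change.** - Add a numbered exclusion to 6.3: more than 12 hours from symptom onset, counted from last known well time if onset was unwitnessed, to a stated event. The sponsor must confirm that event. Start of Dose #1 is the practical choice, but it is a design decision, since it accepts that Dose #3 may end at 14.9-15.8 h.
- Word 2.1 to match, for example three doses with the first started within 12 hours.
- Change the CT requirement in 6.1 to no evidence of severe hemorrhage (see 6.3.3) or major trauma, keeping the trauma clause.
- Delete warfarin from the exceptions in 5.6.1.
- Check that the eligibility form used under 7.3 agrees with the amended text.

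The cost is one protocol amendment with the approvals that 11.5 requires from the sponsor, the manufacturer and the IRB. It needs no additional patients or procedures and leaves the planned 24 subjects, the escalation rule and the DLT definition as they are.

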1.0 Background and Rationale

1.1 Background

Stroke is the fifth leading cause of death in the United States and is the leading cause of long term disability^{1,2}. Distinct geographic disparities in stroke mortality, with highest rates in the southeast United States including Arkansas, are known as the “stroke belt.” There the average stroke mortality is \approx 20% to 40% higher than the rest of the nation³. Stroke is the leading cause of serious long-term disability³. Between 2012 and 2030, disability and medical costs related to stroke are projected to triple, from \$71.6 billion to \$184.1 billion, with the majority of the projected increase in costs arising from those 65 to 79 years of age⁴.

There are two main forms of stroke, ischemic and hemorrhagic. An ischemic stroke occurs in 85% of cases and is caused by cerebral vessel occlusion, obstructing blood flow to a portion of the brain¹. Currently, the only approved therapies for acute ischemic stroke are IV tissue plasminogen activator (tPA), a thrombolytic agent that clears the thrombus within the blood vessel, or intra-arterial catheter thrombectomy. Despite the availability of therapy, it reaches only approximately 7% of ischemic stroke victims in the United States⁵. Delay beyond the effective time window for therapy is a common reason for failure. To reduce the devastating impact of stroke on individuals and society, we continue to seek ways to improve functional recovery and limit ischemic damage in stroke patients. The potential neuroprotective agent, dodecafluoropentane emulsion (DDFPe) has recently shown strong positive effects in pre-clinical animal models of acute ischemic stroke⁶⁻¹¹. Other perfluorocarbons have been tested in humans as potential neuroprotectants and blood substitutes¹² yet none have been successful.

DDFPe (2% w/vol) is a liquid perfluorocarbon nanodroplet which transports over 200 times as much oxygen per milligram of fluorocarbon as others tested as oxygen therapeutics¹³⁻¹⁵. It is active at doses that have already been safely tested as bolus IV injections in humans as an ultrasound contrast agent by Sonus Pharmaceutical in over 2200 patients,^{16,17} and was approved by the European Medicines Agency as an ultrasound contrast agent. NuvOx Pharma owns these data and the FDA has given NuvOx guidance that the prior human data from the ultrasound contrast development can be used in support of therapeutic development of DDFPe. NuvOx is currently conducting a Phase Ib/II trial of DDFPe as a radiation sensitizer to reverse tumor hypoxia in glioblastoma¹⁸ and is about to start a study in sickle cell disease for which an IND has been granted. NuvOx has received Orphan Drug Designations for both the glioblastoma and sickle cell disease applications.

This fluorocarbon with its greater innate oxygen carrying capacity and smaller particle size that allows delivery to occluded and ischemic areas is a superior oxygen transporter (OT). DDFPe was shown to significantly improve

functional recovery within two hours of dosing and full recovery by 3.5 hours in the rabbit stroke model⁶. A small dose of 0.1 ml/kg was effective in the animal model and may provide clinical neuroprotection during pre-hospital triage and diagnosis¹⁰. Recent DDFPe studies confirmed its strong capability as a neuroprotectant, which widened the therapeutic window to 9 hours in ischemic stroke rabbit models. In those studies >80% of infarct volume was protected to 24 hours with only 6 doses over the first 9 hours⁷.

1.2 Brief Description of the Investigational Product

DDFPe is an emulsion of 2% dodecafluoropentane in stabilizers (sucrose, PE-Telomer B) and phosphate buffered saline (pH 7.0). Compared to higher molecular weight liquid fluorocarbons that have already been studied extensively as OTs, DDFPe carries far more oxygen per gram of fluorocarbon.

Stoichiometrically, DDFP has 200 times the oxygen carrying capacity compared to human hemoglobin. Consequently, if it were administered intravenously (IV) and passed through the lungs of patients breathing high concentrations of oxygen, it would take up large amounts of oxygen and increase the oxygen concentration in blood in a dose-dependent way. Hypothetically, by shifting ischemic environments to normal tissue pO₂ environments patient recovery from stroke will be improved.

1.3 Preclinical Studies

Extensive work was done to evaluate the toxicity and PK/PD of DDFPe as an ultrasound contrast-imaging agent. During development, most work was done using "activated" dodecafluoropentane emulsion (DDFPe) referred to as EchoGen® when it was studied as a contrast agent. EchoGen was administered as bolus IV injections. Activation was achieved by applying negative pressure (usually by suction in a syringe) which resulted in 2 micron sized microbubbles of gas in the circulation. The "activated" form of DDFPe has been shown to have more toxicity than "unactivated" compound (0.2 micron vesicles of DDFP without microbubbles). Recently, in a single- dose rat study, the maximum tolerated dose of "unactivated" DDFPe was determined to be 6 mL/kg, which converted to a human equivalent dose (HED) of approximately 1 mL/kg. At that dose in the rats, toxicity was observed to be impaired locomotion and blanching of the typical red color of the eyes and gums. No mortality was observed and all animals recovered within 4 hours.

Studies have also been performed in non-human primates. Anaesthetized rhesus monkeys received 0.6 mL/kg of activated DDFPe IV every 30 minutes for 3 doses without adverse effects¹⁹. In addition, conscious cynomolgus monkeys showed no adverse reactions to 0.6 mL/kg of activated DDFPe given IV every 30 minutes for 3 doses and showed only minor transient changes in blood pressure and heart rate at up to 1.1 mL/kg¹⁹.

Additional information on the preclinical evaluation of DDFPe is presented in the Investigator's Brochure.

